**Patient Data:**

Prior to Treatment:

- Patient's name, phone number, gender, age, medical record number (MRN), address including zip code, name of school (if applicable), organized sports activities, and pertinent medical history. Geographic mapping techniques will be used by the Emerging Pathogens Institute at the University of Florida to track MRSA isotypes to specific schools, neighborhoods or zip codes.
- Date and time when wound noticed.

Treatment:

- The date and time of treatment.
- Additional treatments, protocol deviations, techniques, antibiotics, consult, admission, or other comments.

**Data Analysis and Data Monitoring:**

The Statistical package for the Social Sciences (SPSS, v 17.0) will be used for data analysis. Descriptive statistics will be recorded as means  $\pm$  standard deviation or proportions as appropriate. Categorical variables will be compared using Chi-square and continuous variables will be compared with two-sided Student's t tests or analysis of variance as appropriate. For all analyses, a  $p$  value  $< 0.05$  will be considered significant.

**Data Monitoring:** The PI will be notified of all adverse events. There is no data monitoring committee for this study because the risk is low and no adverse events have emerged in previous cases and studies (in vivo and in vitro).

The sponsor employs a doctorally prepared registered nurse, with clinical trial/research experience, who holds an active Florida risk management license. She will provide desk top reviews for adverse events, if any.

**Data Storage and Confidentiality:** Information obtained in this research contains identifying patient information. Data collection forms will be secured in the ED in a locked file cabinet and removed when the patient has completed treatment (abscess in clinical stage 1 or 2) and stored in the PI's office in a locked file cabinet. The PI's office is locked at night assuring a double locked situation. Each unique patient ED visit will be assigned a code. Patient identifiers and key-codes will be kept exclusively within a password and encrypted protected spreadsheet that will be stored on the University of Florida Emergency Department server. Only those directly involved in this research will have access to the study data. Papers stemming from this work will not include identifying patient information. The key code will be destroyed at the end of the study.

**Patient Data Reporting:** The information from the patients will be "de-identified for research purposes" following HIPAA guidelines for the patient's privacy protection (in accordance with 45 CFR 164.502(d) and 164.514(a)-(c) of the Rule). The data will be collected on a paper copy as described above and assigned a unique identifier. De-identified forms will then be scanned and sent digitally to the sponsor.

- **Risk/Benefit Assessment:** Patient involvement in this study presents minimal risk beyond those associated with standard treatment for uncomplicated abscesses. The possibility of hypersensitivity or allergic reaction to Chlorhexidine gluconate exists but it is a dilute, topically applied solution and thus, represents minimal risk. Patients will be monitored for hypersensitivity or allergic reaction to the irrigant solution in the ED.

**Potential Benefit to the Subjects:** Anecdotal evidence suggests that patients currently treated with IrriSept delivery system have more rapid abscess healing than standard of care. It is possible that patients treated with IrriSept delivery system will have more rapid abscess resolution than those not treated with the experimental device.

**Alternatives to Participation:** Participation in this research is entirely voluntary. Subjects electing not to participate will be treated according to the current standard of care, including

I&D of the abscess.

- **Subject Identification, Recruitment and Consent/Accent:**

All patients 12 years and older presenting to the Shands/UF ED who are immunocompetent and meet inclusion criteria will be eligible for participation. Residents, Faculty and Physician extenders in the Shands/University of Florida ED will obtain written informed consent prior to patient enrollment. Eligible subjects will be informed of the study in a private area or treatment bay of the ED and allowed up to 30 minutes to decide on participation. Participation is entirely voluntary and refusal to participate will not affect medical care rendered. There will not be any threat of harm or adverse consequences if the subject does not agree to participate in the study and the information provided during the consent process will be presented in a balanced way with equal emphasis on all elements of consent (e.g. there will not be over-emphasis of benefits or under-emphasis of risks).

Only those who are cognitively able, as determined by triage personnel and the treating physician, to provide informed consent will be approached. Children age 12 years and older will be asked to provide assent and parents will provide written informed consent. Only patients with signed informed consent will be entered into the study. Informed consent documents will be retained in the PI's locked office and file cabinet.

There will be no cost to subjects for participation in the study outside of that incurred for standard of care. Sponsor will provide the study devices. Initial wound culture is part of standard of care. The patient will be mailed a \$50.00 gift card as nominal token of appreciation, once the 48 hour return visit is completed.

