**Research Site:**  
University of Florida/Shands Emergency Department  
College of Medicine  
Department of Emergency Medicine  
[name]  
[name]  
[name]  
[contact]

- **Purpose of the Study and Background:**

**Study Purpose:** The purpose of this study is to *determine the effect of wound irrigation with IrriSept™ delivery system on abscess healing in healthy patients presenting to the Emergency Department (ED).*

The Specific Aims of the Study are:

- 1: To determine if use of pressurized irrigation with IrriSept delivery system in uncomplicated abscesses improves wound healing when compared to pressurized irrigation with normal saline.
- 2: To determine if use of IrriSept delivery system reduces (or eliminates) the need for oral antibiotics in patients with uncomplicated abscesses presenting to the ED.
- 3: To determine if use of pressurized irrigation with IrriSept delivery system in uncomplicated abscesses improves wound healing in patients that have MRSA-positive wounds compared to pressurized irrigation with normal saline.

**Background:** The current standard of care for the ED management of uncomplicated abscesses is to incise and drain (I&D), irrigate, and pack the wound. Oral antibiotics are commonly prescribed despite little evidence to support this practice. Based on published literature on this subject, a 6% to 16% re-infection rate occurs with this standard of care.

Since 2004, Irrimax Corporation has marketed a saline-based product (Max-101) which includes a novel compressible bottle design and splashguard. The product is used in EDs and other acute wound care sites to irrigate wounds with a pressurized dispersed stream of saline. In February 2009, Irrimax Corporation received notice that IrriSept, a new delivery system containing Chlorhexidine Gluconate (CHG), was cleared by the FDA for wound cleansing and debridement.

In early anecdotal studies conducted by Irrimax Corporation, an improvement in healing

rates and signs of infection were observed with use of these products. Most notably, a reduction in exudate from infected abscesses was observed within 24-48 hours of using IrriSept delivery system on wounds.

- **Criteria for Subject Selection:**

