**Number of subjects:** The total number of consented ED subjects will be 628, 314 per arm. With an expected attrition rate of 66% for the return appointments, the total final number, who return for a 48-hour follow-up appointment and complete the entire study, will be 214 (n=214). The current attrition rate of subjects returning to the ED for recheck of uncomplicated abscesses at Shands/University of Florida ED is 66%.

A sample size of approximately 107 subjects in each arm will provide a power of 80% to detect a 20% improvement in subjects treated with IrriSept with an alpha of 0.05.

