- 7: Thoroughly cleanse entire abscess ensuring that exudate is clear and the solution contacts all inner surfaces of the abscess cavity.
- 8: Repeat until 450 cc of irrigant is used and the abscess is clear of exudate.
- 9: Wait at least one minute.
- 10: Rinse the abscess using the same technique as above with an equal volume of normal saline.
- 11: Loosely pack the abscess cavity with plain packing strip.
- 12: Apply a non-occlusive dressing to the wound.

After initial treatment, the physician will complete the patient data collection form through the "treatment" section and ensure that the patient understands the requirements for follow-up return and immediate return for worsening. The patient will follow-up every 48 hours for repeat examination until clinical resolution. This practice of frequent follow-up is consistent with the current standard of care. At each visit, the physician will complete the patient data collection form examining for fever, wound exudate, erythema, induration, warmth, fluctuance, pain, and abscess reformation. If at the first 48-hour evaluation, the patient's abscess is in category 1 or 2 (see Wound Resolution scale below), then the clinical data collection is complete. If the patient is in category 3, 4, or 5, there will be additional data collection every 48 hours until the patient's abscess is in category 1 or 2.

If signs of worsening or systemic infection are present, appropriate antibiotic treatment will be given. If necessary, a surgical consultation will be obtained or the patient will be admitted to the hospital for further treatment. This is at the discretion of the treating physicians.

**Wound Swab and Culture:** The abscess cavity will be cultured at presentation to assess the types of bacteria present with specific testing for MRSA. Wound culture is consistent with the current standard of care. MRSA positive isolates will be sent to the Emerging Pathogens Institute at the University of Florida for DNA fingerprinting and identification of specific MRSA isotypes.

**Data Collection:** Patients will be evaluated at 48 hours and at 48-hour intervals until abscess healing. The wound will be compared to previous data collected for wound exudate, erythema, induration, warmth, fluctuance, and pain. If the patient requires antibiotics, this will be recorded. Results from the wound culture and MRSA culture will also be recorded.

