**Primary Outcome Measures:**

Oral Antibiotics:

Oral antibiotics required at 48 hours?

Yes

No

Wound Improvement:

Wound improvement will be assessed on a 5-point Likert scale using the clinical scale outlined below.

- 1: Clinically resolved, no signs of active infection.
- 2: Markedly improved, resolving infection and healing.
- 3: Improved with some remaining signs of active infection.
- 4: Unchanged, stable without signs of worsening clinical infection.
- 5: Worsening conditions.

Exudate:

Exudate will be assessed using a 5-point Likert scale as outlined.

1 = none

2 = scant

3 = minimal

4 = moderate

5 = copious.

Patient Comfort:

Pain Scale – A subjective patient-assessed measure using a 10 cm Visual Analog Scale.

NO PAIN

MOST SEVERE PAIN

Secondary Outcome Measures:

Erythema – Circle the area of redness surrounding the abscess with a marker at treatment and at follow-up. Measure the longest and shortest axes of the most lateral edges.

Abscess Size:

Initial Measurement: [                    cm] x [                    cm]

1st Follow Up Measurement: [                    cm] x [                    cm]

2nd Follow Up Measurement: [                    cm] x [                    cm]

Warmth –

Yes

No

Fluctuance –

Yes

No

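### The two ordered 5-point primary outcomes fall, on the natural reading, to an unordered chi-square test, which does not test improvement

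*Protocol*

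**What the plan says.** Under Primary Outcome Measures, the protocol lists oral antibiotics (yes/no), wound improvement, exudate and a pain visual analog scale. Two of these are ordered scales:

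- "Wound improvement will be assessed on a 5-point Likert scale using the clinical scale outlined below", running from 1 (clinically resolved) to 5 (worsening).
- "Exudate will be assessed using a 5-point Likert scale as outlined", running from 1 (none) to 5 (copious).

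No cut-off is given for either. Data Analysis and Data Monitoring gives one general rule: "Categorical variables will be compared using Chi-square and continuous variables will be compared with two-sided Student's t tests or analysis of variance as appropriate". It assigns no outcome to a test by name, and it mentions no rank, trend, ordinal or baseline-adjusted method.

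Aim 1 is directional. It asks whether the product "improves wound healing when compared to pressurized irrigation with normal saline". Number of subjects states that "A sample size of approximately 107 subjects in each arm will provide a power of 80% to detect a 20% improvement", at alpha 0.05, without naming the outcome or the control rate.

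Pre-treatment values are collected. Data Collection says "The wound will be compared to previous data collected for wound exudate, erythema, induration, warmth, fluctuance, and pain", and the erythema instruction reads "Circle the area of redness surrounding the abscess with a marker at treatment and at follow-up". Abscess size also has an initial measurement.

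**The concern.** A 5-category scale is a categorical variable, so "Categorical variables will be compared using Chi-square" most naturally means a Pearson chi-square on the 2x5 table with 4 degrees of freedom. Its p value does not change if the five category labels are shuffled. It asks whether the two distributions differ in any way, whereas Aim 1 asks whether healing is better. Two errors follow: a consistent improvement spread over all categories can be missed, and a difference that is no improvement can be significant.

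The phrase "as appropriate" could also admit a t test on the 1-5 scores or a split at categories 1-2. The choice between these could then be made after the data are seen, on a primary outcome.

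A separate and lesser matter is that the stated methods make no use of the pre-treatment exudate, pain, erythema and size. At the first follow-up, the earlier data on exudate and pain can only come from the treatment visit. An unadjusted t test is valid there but gives up precision. No stated power is missed for this reason.

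**Working it through.** **Inputs from the protocol.** 107 completers per arm, 80% power, 20% improvement, alpha 0.05 (Number of subjects); two-sided tests are stated for continuous variables (Data Analysis). Control rates, category shapes and correlations are not given and are assumed below.

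**1. Reproducing 107 per arm.** Two proportions, 40% against 60%, two-sided:

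n = [1.960·√(2·0.5·0.5) + 0.842·√(0.4·0.6 + 0.6·0.4)]² / 0.20² = 96.9

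With continuity correction: n = (96.9/4)·[1 + √(1 + 4/(96.9·0.20))]² = 106.7, that is 107.

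Other control rates for 20 points, corrected: 105.7 at 35% or 45%, 102.8 at 30% or 50%, 90.9 at 20% or 60%. The stated size therefore fits a comparison of two proportions with a control rate near 40%.

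**2. Two worked tables (illustrative counts, 107 per arm, categories 1 to 5).** Control is 16/27/32/21/11 in both.

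*Table A, IrriSept 27/33/26/14/7 (better throughout).* The arms are equal in size, so each expected count is the mean of the two arms. The category contributions to chi-square are 2.81 + 0.60 + 0.62 + 1.40 + 0.89 = 6.32 on 4 df.

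*Table B, IrriSept 28/15/22/20/22 (43 in categories 1-2 in both arms; worsening doubled from 11 to 22).* The contributions are 3.27 + 3.43 + 1.85 + 0.02 + 3.67 = 12.24 on 4 df.

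| Test | Table A p | Table B p |
|---|---|---|
| Chi-square, 2x5 | 0.18 | 0.016 |
| Proportional odds (likelihood ratio) | 0.012 (OR 1.85) | 0.68 |
| Rank-sum | 0.013 | 0.68 |
| t test on scores | 0.015 | 0.65 |
| Category 1-2 split, uncorrected | 0.020 | 1.0 |

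Only the 2x5 chi-square misses the improvement in A, and only it is significant in B.

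**3. Order is ignored.** For 30/34/25/12/6 against 15/28/38/16/10, the chi-square p is 0.043. After shuffling the categories it is still 0.043, while the rank-sum p moves from 0.003 to 0.146.

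**4. Power at 107 per arm.** A consistent shift multiplies every cumulative odds by a common odds ratio. Moving categories 1-2 from 40% to 60% needs OR = (0.6/0.4)/(0.4/0.6) = 2.25. For control (0.15, 0.25, 0.30, 0.20, 0.10), the cumulative 0.15, 0.40, 0.70, 0.90 become 0.284, 0.600, 0.840, 0.953. Trials were simulated (20,000 per scenario, four assumed category shapes) for a 20-point gain in categories 1-2:

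| Control in categories 1-2 | Chi-square, 2x5 | Rank-sum |
|---|---|---|
| 20% or 60% | 87-91% | 97-98% |
| 30% | 77-80% | 92-94% |
| 40% | 73-76% | 90-91% |
| 50% | 78-79% | 92-93% |
| 70% | 99% or more | 99% or more |

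At 40%, the t test on scores has 89-91% and the category 1-2 split 83%. Proportional odds gave 90-91% in two of the shapes (2,000 trials each). At OR 2.0 with control rates of 35-50%, chi-square has 57-61% and rank-sum 79-82%. A separate simulation with three other shapes gave 72-76% against 90-91% at OR 2.25. Type I error was close to 5% for every test.

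**5. Disagreement between readings.** At 40% to 60%, the 2x5 chi-square and the t test on scores disagree on significance in 16-18% of trials (50,000 simulated).

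**6. The order can reverse.** If only two categories change (category 2 from 25% to 45%, category 3 from 30% to 10%), chi-square has 94% power and rank-sum and proportional odds have 31%.

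**7. Baseline adjustment.** The variance factor is 1 − r². For assumed correlations of 0.3, 0.5 and 0.7 it is 0.91, 0.75 and 0.51, a reduction of 9%, 25% and 51%.

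**The case against.** The protocol never says that the two scales go to a 2x5 chi-square. The match of 107 per arm to a two-proportion comparison, and the use of category 1 or 2 as the end of data collection, suggest that a split at 1-2 may have been meant. That test is directional and has 83% power in the 40% to 60% case. A t test on scores is also directional, and both behave well in Tables A and B. This stands as a limit: the power loss belongs to one reading, though the natural one. It does not remove the point. The outcome section defines no such split, the follow-up rule is not an outcome definition, and several admissible readings with different answers are themselves a fault in a primary analysis.

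Test assignment is often left to an SAP, and one may exist. Here, however, the protocol states a rule, and that rule does not suit its own aim.

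The proposed test is not better for every effect shape. In Table B it does not flag the doubling of worsening, and in the two-category case it has far less power. This stands, and it is why the category distribution must be reported. Baseline adjustment is optional in a randomised trial, and the wound-improvement scale already rates change; that part is an improvement in precision, not a correction of an error.

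**Conclusion.** The concern holds, as something that should be changed. On the natural reading, two primary outcomes are tested by a method that ignores the direction named in Aim 1. Under a consistent shift the loss is about 7-22 percentage points of power for control rates of 20-60%, and nil at 70%. Whether chi-square falls below the stated 80% depends on an endpoint and control rate that the protocol does not give. It does so at 35-45%, the rates at which 107 per arm is best explained, and narrowly around 30% and 50%. All of this rests on assumed category shapes and a proportional-odds effect; for an effect confined to single categories the ranking can reverse. Validity in the sense of type I error is not at issue. The baseline point is secondary and would not carry the finding alone.

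**What to change.** Replace the general rule in Data Analysis and Data Monitoring with text such as:

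> Wound improvement and exudate at 48 hours will be compared by proportional-odds regression on treatment (exudate adjusted for pre-treatment exudate), reporting the common odds ratio with 95% CI. The Wilcoxon rank-sum test is a sensitivity analysis, and the category distribution will be shown by arm. Pain VAS, erythema and abscess size (each of the last two as the product of its two recorded axes) will be compared by ANCOVA with the pre-treatment value as covariate. Chi-square is kept for yes/no outcomes.

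The 48-hour visit is proposed because it is the one follow-up that every completer has. If the sponsor did intend a category 1-2 split, it should be defined as an outcome instead. In either case, Number of subjects should say which outcome and control rate the 20% refers to, so that the size and the analysis match.

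The cost is a few sentences and standard software, with no new data. The downside is small: the common odds ratio assumes a consistent shift and loses power when the effect sits in single categories, so showing the distribution by arm is a required part of the change.

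### Four unranked primary outcomes, each judged at p < 0.05 with no success rule: if any one counts, the false-positive chance is about 9% to 19%, not 5%

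*Protocol*

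**What the plan says.** Under Primary Outcome Measures the protocol sets out four outcomes ahead of a separate list of secondary ones:

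- antibiotic need, yes or no: "Oral antibiotics required at 48 hours"
- wound status: "Wound improvement will be assessed on a 5-point Likert scale using the clinical scale outlined below"
- exudate: "Exudate will be assessed using a 5-point Likert scale as outlined"
- pain: "A subjective patient-assessed measure using a 10 cm Visual Analog Scale"

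None is placed above another. Data Analysis and Data Monitoring gives the only decision rule: "For all analyses, a $p$ value $< 0.05$ will be considered significant".

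Number of subjects justifies about 107 evaluable patients per arm with 80% power "to detect a 20% improvement in subjects treated with IrriSept with an alpha of 0.05". It does not say which outcome the improvement refers to, and it gives no control rate.

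The Specific Aims are numbered but are not presented as a testing order. Aim 1 asks whether IrriSept "improves wound healing when compared to pressurized irrigation with normal saline". Aim 2 asks whether it "reduces (or eliminates) the need for oral antibiotics in patients with uncomplicated abscesses presenting to the ED". Aim 3 repeats the healing question in MRSA-positive wounds. No aim names exudate or pain.

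**The concern.** With four primary outcomes, a reader needs to know whether the trial is positive when one succeeds, when all succeed, or when a particular one succeeds. The protocol does not say. Because it calls every p below 0.05 significant, nothing in it prevents one favourable result out of four from being reported as a positive primary finding. On that reading, the 5% error rate behind the sample size does not apply to the trial's main conclusion.

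This is not simply a detail left to a statistical analysis plan. The protocol fixes both the number of primaries and the unadjusted threshold, so a later plan that adjusted for multiplicity would depart from the protocol's own sentence. The choice also has to be made before results are known. Afterwards, nobody can tell a pre-specified primary from the one that happened to succeed.

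**Working it through.** **Inputs.** From the protocol: four primaries (Primary Outcome Measures); threshold 0.05 for every analysis and two-sided t tests (Data Analysis and Data Monitoring); 107 per arm, 80% power, a 20% improvement, 66% attrition and 628 consented (Number of subjects). Assumed, because the protocol does not give them: an any-one-counts rule, equally correlated test statistics with correlation ρ from 0 to 0.9, and a control rate of 40%.

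**1. The protocol's own sample size.** Read the improvement as 20 percentage points, 40% against 60%, which is the rate pair needing most patients:

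n = [1.960 × √(2 × 0.5 × 0.5) + 0.842 × √(0.4 × 0.6 + 0.6 × 0.4)]² / 0.20² = 96.9, so 97 per arm.

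With continuity correction: (96.9 / 4) × [1 + √(1 + 4 / (96.9 × 0.20))]² = 106.7, so 107 per arm.

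On these assumptions the stated figure is reproduced as one test using the whole 0.05. For attrition, 628 × 0.34 = 213.5, in line with the stated 214.

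**2. Chance of at least one false positive, four true null hypotheses.** If independent: 1 − 0.95⁴ = 0.1855. With common correlation ρ,

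1 − ∫ φ(u) [Φ((c − √ρ u)/√(1 − ρ)) − Φ((−c − √ρ u)/√(1 − ρ))]⁴ du, with c = 1.960.

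The benefit-only column drops the lower-tail term (2.5% per test). The three-outcome column uses power 3 in place of 4, for the case where antibiotics are judged alone under Aim 2; at ρ = 0 it is 1 − 0.95³ = 0.1426.

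| ρ | Four outcomes, either direction | Four outcomes, favouring IrriSept only | Three outcomes, either direction |
|---|---|---|---|
| 0 | 18.5% | 9.6% | 14.3% |
| 0.3 | 17.4% | 8.7% | 13.6% |
| 0.5 | 15.6% | 7.8% | 12.5% |
| 0.7 | 13.0% | 6.5% | 10.9% |
| 0.8 | 11.4% | 5.7% | 9.8% |
| 0.9 | 9.4% | 4.7% | 8.4% |

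The nominal values are 5%, 2.5% and 5%. Even at ρ = 0.95 the first column is 8.0%, and at 0.99 it is 6.3%.

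**3. Does the remedy hold the error?** In a simulation with no effect on any outcome (400,000 draws), fixed-order testing gave 5.0% for ρ from 0 to 0.9. Holm gave 4.9% at ρ = 0 and 2.5% at ρ = 0.9.

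**4. Cost if all four stay primary under Holm.** The first step is at 0.05 / 4 = 0.0125. With 40% against 60% and 107 per arm:

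| | Without continuity correction | With |
|---|---|---|
| Power at 0.05 | 83.8% | 80.1% |
| Power at 0.0125 | 66.9% | 61.7% |
| n per arm for 80% at 0.0125 | 138 | 148 |
| Consented at 66% attrition | 2 × 138 / 0.34 = 812 | 2 × 148 / 0.34 = 871 |

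For other 20-point differences (control rate 20% to 60%), power at 0.0125 runs from 62% to 76%.

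**The case against.** The strongest objection is that the protocol never says one significant primary makes the trial positive. Its sentence concerns individual comparisons, each of which keeps its 5% error, and if all four had to succeed there would be no inflation. That is correct, and the 9% to 19% is conditional for that reason. But no all-must-succeed rule is stated. If it were, the power statement, built on one comparison, would not describe the chance of trial success: with an assumed 80% for each outcome and independence, all four succeed only 0.8⁴ = 41% of the time.

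The correlation is also unknown, and the lower end of the range is a choice. A high value has some support for wound status and antibiotics, since Methods and Procedures ties antibiotic treatment to signs of worsening. That argument does not extend to patient-rated pain. This makes the 9% end uncertain without removing the inflation; only near-perfect correlation returns the error to 5%.

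The aims could be read as separate questions, with exudate counted as a measure of healing because the Background singles out reduced exudate as an early observation. That shrinks the family but still leaves several measures sharing one 0.05.

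Finally, the Holm sample sizes are for 80% power on one specified outcome at the strictest step. Under an any-one rule, with all four outcomes sharing the assumed effect (61.7% power each at 0.0125), 107 per arm gives at least one Holm rejection with probability 98% at ρ = 0 and 74% at ρ = 0.9. So 812 or 871 is an upper-end cost for that option and does not bear on the main remedy.

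**Conclusion.** The concern holds and should be fixed before the data are unblinded. As written, the outcome list, the significance rule and the sample size do not together define a positive trial. That conclusion follows from the text alone. The size of the error depends on two assumptions: that any one primary counts, and a common correlation between 0 and 0.9. Under these, the false-positive chance is about two to nearly four times the nominal rate. Setting antibiotics apart under Aim 2 lowers it to between 14.3% and 8.4%, still above 5%.

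**What to change.** **Preferred.**

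- In Primary Outcome Measures, designate one primary outcome. The choice is the sponsor's, and it should be the outcome for which 107 per arm was calculated. Wound improvement at 48 hours is a reasonable candidate because it serves Aim 1.
- State the form in which it will be analysed, for example categories 1–2 against 3–5 by chi-square if the sample size is for a proportion.
- In Number of subjects, name the same outcome and its control rate.
- List the other three as key secondary outcomes in a pre-specified order, each tested at two-sided 0.05 only if the one before it was significant.
- In Data Analysis and Data Monitoring, replace the blanket threshold with this order and label all other p values descriptive.

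**Cost.** Protocol wording only, with no additional patients. A lower-ranked outcome, including antibiotic need (Aim 2) if it is placed below another, cannot be claimed when an outcome above it fails.

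**Alternative.** Keep all four as primary, test them with Holm, and restate power for each in its own form (binary, 5-point scale, visual analogue scale). On the assumed 40% against 60%, guaranteeing 80% power for a specified binary outcome at the first step needs 138 to 148 per arm, or about 812 to 871 consented, against 628.
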